It is a pilot single-blind two-arm parallel randomised control trial that aims to assess the differences between two bone substitutes, natural versus synthetic. The study will mimic the routine practice, and patients will be randomly allocated to receive either the natural (control) or synthetic (intervention) bone substitutes. The patient follow-up period will be 24 weeks from the baseline data collection point.

Methods

Study setting

The study will be conducted in dental clinics in the Midlands, Southeast England and Northwest England.

Eligibility criteria for participants

Inclusion criteria

Adult patients (age >18) in need of extraction of a single-rooted tooth attending the clinics selected for the study

Single units in a dentate patient

Non-surgical extraction – no flap raised, and no bone removed

Intact socket walls post-extraction

Bleeding sockets

Stable periodontal health

ASA Class I or II patients. The American Society of Anaesthesiologists (ASA) classification is a system of physical status evaluation developed to offer clinicians a simple categorisation of a patient's physiological status to help predict operative risks (Appendix 1).

Exclusion Criteria

Multiple adjacent extractions

Presence of active periodontal disease

Socket walls not intact - >50% bone loss in any of the four walls

Sclerotic sockets post-extraction – the socket does not fill up with blood post-extraction

Denture wearer – the extraction socket site under the load of a denture

Patients on medication that can affect bone healing e.g., bisphosphonates (oral or intravenous), selective serotonin reuptake inhibitors (SSRI), methotrexate, proton pump inhibitors (PPI)

Uncontrolled diabetes

Smokers

Immunosuppressed Patients

Patients with a history of myocardial Infarction in the last year

ASA Class > II patients (17)(Appendix 1)

Intervention

The test bone substitute is Bonalive[®], bioactive glass S53P4, which contains SiO₂, Na₂O, CaO, and P₂O₅ (granule size 0.5-0.8mm) (18) Bonalive[®] is osteoconductive, meaning that it has the ability of promoting bone growth across the granules and the grafting area and slowly replace it with new bone over time. Bonalive[®] is osteostimulative and has antibacterial properties (19).

Comparator

The comparator is Bio-Oss[®], deproteinized bovine bone granules (granule size 0.25- 1mm) (20). Bio-Oss[®] is osteoconductive, which means it acts as a scaffold only for new bone to grow (21,22).

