Both products have a low substitution rate and are expected to have similar ridge support and shape maintenance capability.

Management of the bone substitutes

The bone substitutes will be used according to the manufacturers' instructions and protocols (Appendix 2 and 3). The materials are supplied in sealed sterile packaging with clearly displayed expiry dates, LOT numbers and CE marks. The materials' LOT numbers and expiry dates will be recorded on the patient records and on a separate 'Surgery Logbook' with an identification number for the patient traceable to the appropriate batch of materials.

The use of the material will follow standard surgical protocols and excess material will be discarded according to clinical waste guidelines.

Clinical procedure

The bone substitute will be used according to the ridge preservation protocol, which will be standardised between the different centres. As part of standard clinical practice, a periapical radiograph will be taken before an extraction. Following the removal of a tooth, the inflamed area of the socket will be curetted to ensure a 'clean' socket. The case will be excluded if:

- The socket walls are very sclerotic with a lack of fresh bleeding, which is essential for healing.
- The socket walls are damaged. The limit is a loss of 50% or more of one of the walls. The assessment of the extraction socket will be done by the clinicians performing the procedures (23).

The bone substitute will then be introduced using a standard sterile protocol, with gentle packing of the material in the sockets to ensure the material reaches the apex of the socket but is not condensed with pressure. The socket will then be sealed with a collagen matrix with non-resorbable sutures. Review appointment for suture removal will be required 2 weeks post-procedure.

Patients will be advised not to fly for two weeks post-procedure or until after the clinicians have reviewed them. Intra-oral scans or impressions with clinical photographs will also be taken on the day the procedure is carried out. The follow-up will take place 24 weeks post-procedure, when a PA radiograph, intra-oral scans or impressions, clinical photographs and a minimally invasive trephine biopsy will be carried out.

Management of tissue samples in the dental clinic

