Recruitment will be focused on private dental clinics in the Midlands, Southeast England and Northwest England

Clinicians: Experienced Implant surgeons at centres approved by lead researchers. Approval will be based on appropriate clinical setup, clinician experience and patient volume.

Patients: Patients who meet the inclusion criteria will be invited to take part in the study. They will consent to using either of the bone substitute materials and be randomly allocated to a group.

Recruitment will start as soon as ethics approval has been granted.

The recruitment strategy will increase potential participants' awareness of the health problem being studied and its potential impact on their health.

Clinician-patient ratio

The patients will be spread across 2-4 surgeries to ensure we meet the target sample size in a few months.

Randomisation, sequence generation, allocation and blinding

The randomisation, sequence generation and allocation concealment will be performed using the sealed envelope online system (<https://www.sealedenvelope.com/>) (32) . The randomisation will be 1:1. The patient will be the unit of randomisation and intervention.

All patients receiving the bone substitutes will be blinded to the treatment in our study. However, patients will know which bone substitute they have received after their final review at 24-week follow-up.

Data collection

Clinicians will collect data at baseline and at 24-week follow-up using a paper template. Then data will be transferred into Excel and SPSS and prepared for the data analysis. All paper records, except consent forms, will be destroyed at patients' last visit. Secure and irreversible destruction processes will include shredding and disposal of records using the University's confidential waste service.

Data management

The procedure will be conducted using the data management template provided by UKRI. Data will be managed following the procedure used in previous studies (26,28). Input data will

be saved and stored on a password-protected system. Only individuals authorised by the CI will be allowed to access the data. Paper data, such as Patients' informed consent will be kept in a locked cabinet by the clinicians.

Statistical methods

The primary analysis will be the intention-to-treat (ITT), including all randomised participants in the assigned group, regardless of their adherence to the protocol or their withdrawal.

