Missing data will be assessed and treated using multiple imputations if missing at random (MAR).

To check for normality, each variable will be analysed using the Shapiro-Wilk test.

Primary outcome

The primary outcome is the difference between the two bone substitutes, natural (Bio-Oss[®]) and synthetic (Bonalive[®]), in preserving the alveolar ridge dimensions assessed by changes in the width of the alveolar ridge (expressed in millimetres) from augmentation (baseline) to 24-week post augmentation. It is expected to be a continuous variable, therefore, the comparison between groups at 24 weeks will be performed using a linear regression model (ANCOVA), including the baseline measurements as the covariates. The recent literature suggests using of ANCOVA as the statistical method of choice for the analysis of intervention effect and adjustment for baseline variables for three reasons: efficiency, precision and power (33).

Secondary outcomes

- The changes in the height of the alveolar ridge (expressed in millimetres) from grafting (baseline) to 24-week follow-up (post grafting) assessed using either intra-oral scanners or impressions and clinical photographs. It is expected to be a continuous variable; therefore, the comparison between groups at week 24 will be performed using the unpaired t-test for a normally distributed variable or the Mann-Whitney U test for non-normally distributed.
- The changes in vertical crestal bone levels between the groups (expressed in millimetres) will be compared using an unpaired t-test or Mann-Whitney U test according to the variable distribution. This will be assessed using radiographs pre-extraction and at 24-week follow-up.
- Presence of bone will be assessed using biopsy used for histology (qualitative assessment of bone infiltration) and PCR to determine the concentration (in nanograms) of gene expression of the bone markers (including osteopontin and osteocalcin).

- The comparison of the concentration of gene expression between the groups at 24-week will be performed using the unpaired t-test for a normally distributed variable or the Mann-Whitney U test for non-normally distributed

Data monitoring

This trial is designed to minimise the risk, as demonstrated in the previous trials by Rignon-Bret et al. (28) and Solakoglu et al. (26). Therefore, no formal committee has been organised, and no interim analysis of the impact of the intervention has been planned.

Risk and safety issues

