Declaration of interest

None

Dissemination policy

The dissemination of the study will begin immediately with the publication of the protocol. The results of this trial will be presented at national and international conferences. They will be submitted as scientific manuscripts to peer-reviewed journals. The trial results aim to inform patients, policymakers, and all other stakeholders that might benefit from the results.

The results of the trial will be disseminated to service users and their families via media, to healthcare professionals via professional training and meetings, and researchers via conferences and publications. The publications generated by this study may be used as training materials for dentists with an interest in implantology.

Ancillary post-trial care

We are not envisaging the need for the provision of post-trial care. Nevertheless, all participants will be provided with an emergency contact number to reach the study

investigators so that they can receive the necessary support when they have any questions or problems.

Patient and Public Involvement (PPI)

The research protocol was developed during the COVID Omicron wave, February-March 2022, thus it was impossible to reach the patients and members of the public and get their input into the protocol.

Discussion

Following the extraction of teeth their supporting alveolar bone undergoes remodelling, which can result in the loss of height and width of the bony ridge; this is most marked in the aesthetic zone (anterior aspect of the upper jaw, the maxilla) (34,35).

To minimise this loss of ridge volume, the ridge preservation technique has been developed, which involves the insertion of bone substitute material to act as a space maintainer and scaffold for new bone growth (36–38)

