The commonly used materials include bovine bone, human-donated bone and synthetic materials (6,38). There is a growing demand for non-animal products and the current synthetic materials have a high substitution rate which defeats the purpose of maintaining the space over periods longer than 4 to 5 months(10,12) . Bioactive glass (BAG) is a synthetic material with a low substitution rate, and antibacterial properties and is widely used by orthopaedic and ENT surgeons, but not yet by dental implant surgeons (13,14). This study aims to investigate whether the BAG material can be as effective or more effective as the bovine bone material as a bone substitute in implant dentistry. The importance of this study lies in its potential to facilitate a good ridge preservation and prevent more complicated augmentation procedures due to the loss of ridge volume in cases such as those listed below:

1. Aesthetic zone when immediate or early (4-8 weeks) placement is not possible (39)
2. Posterior maxilla – roots close to the floor of the sinus (40)
3. Posterior mandible – roots close to inferior dental canal/ mental foramen
4. Pontic area for aesthetics of the bridge
5. Extraction of the tooth adjacent to the implant
6. Large socket e.g., a molar with septal bone loss leaving a wide defect

In addition to the ridge preservation, benefits of BAG include reducing the risk of more complex, expensive, and risky augmentation procedures. The use of BAG can benefit patients undergoing sinus augmentation procedures, as well as the treatment of peri-implantitis (infection and bone loss around dental implants) due to its osteoconductive, osteostimulative, and antibacterial properties. .

Conclusion

Ridge preservation is a well-documented technique for maintaining the bone volume of the alveolar ridges of the jaws. This study will assess the effectiveness of the use of the synthetic material BAG which presents no cross-infection risk and has documented antibacterial properties and the desired low substitution rate. The results of this pilot study will provide the essential information to design a full-scale RCT and apply for funding too. Furthermore, the results of the pilot could be considered as the basis of further research into BAG use for general augmentation and in the treatment of peri-implantitis.

Protocol version

2.0

Funding

Not funded

Acknowledgements

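### Does the ridge-width ANCOVA need a tooth-position term because the protocol links ridge loss to tooth position?

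*Combined protocol and SAP*

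**What the plan says.** Under Statistical methods, Primary outcome, the between-group comparison of ridge width at 24 weeks "will be performed using a linear regression model (ANCOVA), including the baseline measurements as the covariates". Efficiency, precision and power are given as the reasons for choosing ANCOVA. Tooth position is not mentioned there.

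Under Randomisation, sequence generation, allocation and blinding: "The randomisation will be 1:1. The patient will be the unit of randomisation and intervention". No stratification factor is named, and the reference cited for the online service is titled as a simple randomisation service.

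The inclusion criteria admit adults "in need of extraction of a single-rooted tooth", with no limit to one jaw or region. On loss of ridge height and width after extraction, the Discussion states that "this is most marked in the aesthetic zone (anterior aspect of the upper jaw, the maxilla". Its next paragraph begins: "To minimise this loss of ridge volume, the ridge preservation technique has been developed".

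The Comparator section says of the two materials: "Both products have a low substitution rate and are expected to have similar ridge support and shape maintenance capability". Under Clinical procedure, the substitute is used "according to the ridge preservation protocol, which will be standardised between the different centres".

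The Sample size section sets 34 participants, 17 per group, on pragmatic grounds. It says the pilot will supply the inputs for sizing the full trial, the standard deviation among them.

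**The concern.** The protocol seems to name a strong predictor of its own primary outcome and then ignore it twice, in the allocation and in the model. Any single-rooted tooth is eligible, so position can vary, and with 17 per arm and no stratification the arms may differ in it by chance. The reasons given for adjusting for baseline would seem to apply equally to position.

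Three things would be at stake: a treatment estimate shifted by chance imbalance, a confidence interval wider than necessary, and a residual SD too large for planning a full trial that adjusts for position.

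**Working it through.** **Inputs from the documents.** N = 34, 17 per arm (Sample size); 1:1 allocation, no strata; ANCOVA with arm and baseline. There is no power calculation to reproduce: 2 × 17 = 34, and 17 lies within the 15 to 20 per group that the section cites.

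**Assumptions, because the documents give no figures.** Share of anterior maxillary teeth p = 20% to 50%; position effect beyond baseline width g = 0, 0.5 or 1 residual SD; baseline slope 0.7; two-sided 5% level.

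**1. Validity of the planned analysis.** Position is fixed before allocation, so randomisation makes it independent of arm. Leaving it out adds noise but no systematic error. In simulations without a treatment effect, the mean error of the baseline-only estimate was within 0.003 SD, and rejection over all trials was 4.8% to 5.4%.

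**2. Effect on the confidence interval.** The term takes one residual degree of freedom (34 - 3 = 31 becomes 30), and the critical t value goes from 2.040 to 2.042. It breaks even when

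(t₃₀/t₃₁) × √(1 + 1/31) = √(1 + g²p(1 - p)).

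The left side is 1.00135 × 1.0160 = 1.0174, whose square is 1.0351. Hence g = √(0.0351/[p(1 - p)]):
- p = 20%: √(0.0351/0.16) = 0.47 SD
- p = 50%: √(0.0351/0.25) = 0.37 SD

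Below those values the term widens the interval on average. Simulated change in mean width:

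| Position effect | Change in mean CI width |
|---|---|
| 0 | +1.8% |
| 0.5 SD | -0.2% to -1.3% |
| 1 SD | -5.2% to -9.0% |

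At 0.5 SD the interval with the term was the wider one in 48% to 59% of trials.

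**3. Effect on the planning SD.** Ratio of the baseline-only SD to the position-adjusted SD = √(1 + g²p(1 - p)):
- 0.5 SD: √1.04 = 1.02 to √1.0625 = 1.03, so the full-trial N is 4% to 6% larger
- 1 SD: √1.16 = 1.08 to √1.25 = 1.12, so N is 16% to 25% larger

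The 95% confidence limits for an SD on 31 degrees of freedom are -20% and +33%. Even the 1 SD case lies well inside the pilot's own uncertainty.

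**4. Can fitting both models show which SD to use?** Simulation used 17 per arm, shares of 20%, 30% and 50%, and 8,000 trials per cell:
- with a true 0.5 SD effect, the adjusted residual SD came out larger than the unadjusted one in 34% to 44% of pilots
- with no effect, it came out smaller in 32% to 33%
- power to detect the position term at 0.5 SD was 19% to 27%

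One fit at N = 34 therefore cannot settle the choice. The full trial's planned model settles it.

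**5. Chance imbalance.** For two independent Binomial(17, p) counts, the probability of a gap of 4 or more teeth is 0.130, 0.189, 0.220 and 0.230 for p = 20%, 30%, 40% and 50%. Within that minority of trials, the baseline-only false-positive rate is 5.8% to 6.5% at 0.5 SD and 8.6% to 9.4% at 1 SD. Trials with smaller gaps offset this, which is why the overall rate in step 1 stays near 5%.

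**6. What supports a sizeable effect?** The sentence on the anterior maxilla concerns remodelling after extraction in general. The next paragraph presents grafting as the means of limiting that loss, and every participant is grafted. Baseline width, already in the model, may also carry part of any position effect.

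The share of anterior teeth is equally open. The Discussion's list of situations in which ridge volume is at risk ("due to the loss of ridge volume in cases such as those listed below") describes where the technique could help, not who will be enrolled; it includes a molar, while the trial takes single-rooted teeth. At an assumed share of 90%, the probability of a gap of 4 or more falls to 4% and break-even rises to 0.62 SD.

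**The case for a change.** The strongest case for adding the term is that it costs almost nothing. A single pre-specified supportive model would leave the primary analysis and N untouched, would cost about 1.8% of interval width at worst on average, and would show whether imbalance in position moves the estimate. It would also give an SD for a full trial that adjusts for position. Timing matters as well: the protocol expects no change to the analyses, and paper records other than consent forms are destroyed at the last visit.

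Parts of this stand. Position is not used in allocation and is not named in the model. A gap of 4 or more teeth is quite possible at the assumed shares. An SD for a position-adjusted full trial does require that position be recorded.

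The rest does not make the plan deficient. The data template is not among the documents, so they do not show that position goes unrecorded. If it is recorded, the adjusted SD can be calculated afterwards without a pre-specified model. The cost is also somewhat more than one sentence: with multiple imputation planned, a model that uses position should have position in the imputation model too. Finally, the conditional false-positive rate of about 9% needs both an uncommon imbalance and a 1 SD effect, in a pilot meant to inform a later trial.

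**Conclusion.** The concern does not hold. The baseline-adjusted ANCOVA is a sound primary analysis under 1:1 randomisation: unbiased on average, with type I error near 5% at every position effect examined. At an effect of 0.5 residual SD the term would change mean interval width by about 1% or less in either direction of practical interest, and the planning SD by 2% to 3%, against an uncertainty of -20% to +33% in that SD. Gains of 5% to 9% in interval width need an effect of about 1 SD beyond baseline width in grafted sockets, for which the documents offer no evidence.

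These figures rest on assumed anterior shares of 20% to 50% and assumed effect sizes. The validity of the planned analysis rests on neither. Whether to add a supportive model with 17 per arm is a trade-off on which statisticians may reasonably differ, and it would change neither the primary result nor the conclusion.

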(12) The allografts (human origin) also have a high substitution rate. It is important to have a low substitution rate to maintain the shape and volume of the jaw ridge for the long term to have a stable result.

Bioactive glass synthetic bone substitute (Bonalive®) is a material that has been shown to have a low substitution rate and antibacterial properties. It has been used successfully in the orthopaedics, craniofacial and ear nose and throat (ENT) specialities for the treatment of osteomyelitis, sinusitis and bony cyst cavities (13,14). There have also been a few maxillofacial surgery case reports (15,16) on its usage in the jaws. However, to the best of our knowledge, the applicability of this material in implant dentistry has not been reported in the literature.

Aim

To investigate the effectiveness of two low substitution rate bone substitutes, natural (Bio-Oss®) and synthetic (Bonalive®) in preserving the alveolar ridge of single-rooted teeth following extraction.

Key research questions

Is there a difference between natural (Bio-Oss®) and synthetic (Bonalive®) bone substitutes in preserving the alveolar ridge dimensions based on:

- I. Changes in the width of the alveolar ridge (expressed in millimetres) from augmentation (baseline) to 24-week follow-up (post augmentation).
- II. Changes in the height of the alveolar ridge (expressed in millimetres) from augmentation (baseline) to 24-week follow-up (post augmentation).
Both changes will be assessed using intra-oral scanners (this does not involve radiographs) or impressions with clinical photographs.
- III. Changes in the vertical crestal bone level assessed in millimetres, using the periapical radiographs taken pre-extraction and at 24-week follow-up and intra-oral scanners (this does not involve radiographs) or impressions with clinical photographs
- IV. Presence of bone around the alveolar ridge assessed using biopsy (up to 3mm diameter by 8mm length) of the centre of the augmented socket. The biopsy sample will be used for histology (qualitative assessment of bone infiltration) and PCR to determine the concentration (in nanograms) of gene expression for bone markers (including osteopontin, osteocalcin) at 24-week follow-up (post augmentation).

Trial design

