The primary outcome is the difference between the two low substitution rate bone substitutes, natural (Bio-Oss[®]) and synthetic (Bonalive[®]), in preserving the alveolar ridge dimensions assessed by changes in the width (expressed in millimetres) from augmentation (baseline) to 24-week post augmentation. Assessment will be done using intra-oral scanners (this does not involve radiographs) or impressions and clinical photographs.

Secondary outcomes

- Changes in height (expressed in millimetres) from augmentation (baseline) to 24-week post augmentation. Assessment will be done using the periapical radiographs taken pre-extraction and at 24-week follow-up and intra-oral scanners (this does not involve radiographs) or impressions and clinical photographs.
- Changes in the vertical crestal bone level (expressed in millimetres) assessed with periapical radiographs taken pre-extraction and 24-week post augmentation. The technique used for this assessment will be the same as that used by Solakoglu et al.(26) to evaluate changes in the alveolar bone crest in similar research.
- Presence of bone around the alveolar ridge assessed using a biopsy, histology (qualitative assessment of bone infiltration) and PCR to determine the concentration (in nanograms) of gene expression for bone markers (including osteopontin, osteocalcin) at 24-week post augmentation.

Sample size

According to Charles et al. (27) four factors are required to calculate the sample size: significance level, power, difference between groups and standard deviation. However, considering the limited availability of information in this area (only one study was identified conducted by Rignon-Bret et al.(28)

The research team, supported by the advice provided by statisticians, decided to conduct a pilot study. Even though a pilot study does not require sample size calculation using the aforementioned four factors, (29) 15 to 20 participants per group are required to ensure the scientific validity of the pilot study results (30). More recently, further information has been provided for the validity of the results of pilot RCT indicating a wider range of participants (31). Therefore, we used a pragmatic approach informed by the literature and we will recruit a total of 34 participants with 17 per group. The results of the pilot study will generate the four factors to calculate the sample size for the full-scale RCT.

Recruitment

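### Change in ridge height and crestal bone level is tested without a baseline covariate and without a stated reason, although width gets ANCOVA: a possible precision loss of unknown size on the t-test branch

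*Combined protocol and SAP*

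**What the plan says.** All the analysis text is in the combined protocol and SAP, under Statistical methods.

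- **Width (Primary outcome).** A linear regression with the baseline measurement as covariate. The section says that recent literature favours "ANCOVA as the statistical method of choice for the analysis of intervention effect and adjustment for baseline variables for three reasons: efficiency, precision and power".
- **Height (Secondary outcomes).** The outcome is change from grafting to week 24, and "the comparison between groups at week 24 will be performed using the unpaired t-test for a normally distributed variable or the Mann-Whitney U test" if it is not normal.
- **Crestal bone level (Secondary outcomes).** The changes "will be compared using an unpaired t-test or Mann-Whitney U test according to the variable distribution".
- **Choice of branch.** A Shapiro-Wilk test on each variable.

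Width and height are both introduced as expected continuous variables, yet they get different models. Nothing elsewhere adds a baseline term for height or crestal level or explains its absence.

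The baseline images exist. Clinical procedure provides a periapical film before extraction and a scan or impression on the day of the procedure. The sections differ, however, on which image yields each outcome:

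- **Height.** Statistical methods has it "assessed using either intra-oral scanners or impressions and clinical photographs", and Key research questions I and II agree. Outcomes, Secondary outcomes, adds films: "Assessment will be done using the periapical radiographs taken pre-extraction and at 24-week follow-up and intra-oral scanners".
- **Crestal level.** Outcomes has it "assessed with periapical radiographs taken pre-extraction and 24-week post augmentation", and Statistical methods agrees. Key research question III adds scans or impressions: "Changes in the vertical crestal bone level assessed in millimetres, using the periapical radiographs taken pre-extraction and at 24-week follow-up and intra-oral scanners".
- **Crestal technique.** It is deferred to a cited trial: "The technique used for this assessment will be the same as that used by" that trial's authors. The documents do not say whether this gives a baseline level in mm or only a reading of change between films.

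**The concern.** A plan that prefers ANCOVA for its precision would be expected to use it for the other two dimensional outcomes, or to say why not. With 17 per arm, chance baseline differences between arms are not small. A change score corrects for such a difference with a fixed slope of 1, whereas ANCOVA estimates the slope. Where the true slope is not 1, the t-test on change is less precise and its estimate moves with the imbalance. At stake is the width of the confidence intervals for two secondary outcomes of a pilot that is meant to supply planning values for a full trial. No decision in the plan rests on either test.

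**Working it through.** **Inputs.** From Sample size: 34 participants, 17 per group (2 x 17 = 34). The size is pragmatic. No significance level, power, effect or SD is given, so there is no power figure to reproduce. Assumed, because the documents give neither: rho, the correlation of baseline with week 24, and k = SD24/SD0. Baseline SD is the unit.

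**Step 1, chance imbalance.** The SE of the baseline difference D between arms is sqrt(2/17) = 0.343 baseline SD.

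**Step 2, variances on the t-test branch.**
- Change score: proportional to k^2 + 1 - 2k·rho.
- ANCOVA: proportional to k^2(1 - rho^2), times 1 + 1/(34 - 4) = 31/30 on average over randomisations, for estimating the slope.
- SE ratio (ANCOVA/change) = sqrt[ k^2(1 - rho^2)(31/30) / (k^2 + 1 - 2k·rho) ].

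Example, k = 1, rho = 0.5: sqrt(0.75 x 31/30 / 1) = 0.880, a 12% cut.

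| rho | k = 0.8 | k = 1 | k = 1.25 |
|---|---|---|---|
| 0.5 | 0.768 | 0.880 | 0.961 |
| 0.7 | 0.805 | 0.937 | 1.007 |
| 0.8 | 0.813 | 0.964 | 1.017 |
| 0.9 | 0.793 | 0.991 | 0.991 |
| 0.95 | 0.733 | 1.004 | 0.916 |

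**Step 3, what ANCOVA can cost.** Since k^2 + 1 - 2k·rho = k^2(1 - rho^2) + (1 - k·rho)^2, the ratio never exceeds sqrt(31/30) = 1.017, reached when k·rho = 1. That is an average. For a realised imbalance of z standard errors the ANCOVA variance factor is 1 + z^2/32. With z = 2 it is 1.125, so the SE is sqrt(1.125) = 1.061 times that of the change score when k·rho = 1.

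**Step 4, sensitivity to imbalance.** Given D, the change-score estimate shifts by -(1 - k·rho)D. For D = 0.343 and rho 0.5, 0.7, 0.8, 0.9, in baseline SD:
- k = 1: -0.171, -0.103, -0.069, -0.034
- k = 0.8: -0.206, -0.151, -0.123, -0.096
- k = 1.25: -0.129, -0.043, 0, +0.043

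This is the (1 - k·rho)^2 term of Step 3 seen another way. It is the same loss, not a second one.

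**Step 5, non-normal data.** Simulated power with 40,000 trials per setting, k = 1, a normal baseline, an effect of 0.99 SD of change and two-sided 5%:

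| rho, residuals | t-test on change | Mann-Whitney on change | ANCOVA |
|---|---|---|---|
| 0.7, normal | 80.2% | 78.0% | 85.0% |
| 0.7, t(3) | 84.1% | 91.2% | 87.9% |
| 0.7, lognormal | 84.3% | 97.5% | 86.9% |
| 0.5, normal | 79.8% | 77.2% | 88.5% |
| 0.5, t(3) | 83.4% | 89.1% | 90.2% |
| 0.5, lognormal | 84.0% | 95.1% | 89.3% |

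Type I error was between 0.039 and 0.051 throughout. The plan's full rule was also simulated, with Shapiro-Wilk applied per arm at 5% (an assumption). At rho 0.7, planned rule against ANCOVA: normal 81 v 85%, t(3) 90 v 87%, lognormal 97 v 87%.

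**The case against.** The best defence is that nothing here is an error. Both tests are valid under randomisation, a change score is a recognised use of the baseline, and the argument for ANCOVA stands under the primary outcome only. The plan never commits to it for every outcome. All of that stands, and it is why the point is one of unexplained inconsistency and possible cost.

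A second defence is that the rule as a whole adapts to the data. This also stands: with heavy-tailed or skewed residuals at rho 0.7 it beats least-squares ANCOVA. A reader might infer that ANCOVA should replace both tests whatever the distribution. The simulations do not support that.

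Three other strong readings are tempting.

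- **That a loss is established.** It is not. Neither rho nor k is documented, and several cells of the table show no gain or a slight cost.
- **That raw week-24 values are compared.** That would lose more: the variance ratio (1 - rho^2)(31/30) is 0.775 at rho 0.5 and 0.372 at rho 0.8. The outcome in each bullet is a change, however, so the wording favours the change-score reading.
- **That the measurement conflicts show the test choice to be wrong, or that no crestal baseline exists.** They are separate matters of outcome definition. Table 1 marks crestal bone at week 24 only, but the pre-extraction film is stated in several sections. What is unsettled is whether a level in mm is read from it.

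**Conclusion.** The concern holds as a minor one. Two secondary outcomes of a pilot are tested without the baseline term that the same section recommends for width, and no reason is given. On the t-test branch this may cost precision. Over rho 0.5 to 0.95, ANCOVA's effect on the SE runs from a 12% cut to no gain at k = 1, is a cut of about 19 to 27% at k = 0.8, and runs from an 8% cut to a 2% increase at k = 1.25. These figures assume normal data, 17 analysed per arm, and values of rho and k that the trial itself would have to supply. The covariate is available for height once its measurement is settled, and for crestal level only if a baseline value in mm is read.

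**What to change.** 1. **First, reconcile the measurement.** Make Key research questions, Outcomes and Statistical methods agree on how height and crestal level are measured, so that each covariate is the same measurement as its outcome.
2. **Height, t-test branch.** Replace the unpaired t-test with the linear model already used for width: the 24-week value on arm plus baseline height by the same method. Report the adjusted mean difference in mm with its 95% CI, the residual SD and the baseline to week-24 correlation.
3. **Crestal level, t-test branch.** Do the same only where a baseline value in mm is read from the pre-extraction film. If change is read only by comparing films, keep the planned test and say so.
4. **Non-normal distribution.** Keep the planned rank test, and report the adjusted estimate and CI beside it where the covariate exists.
5. **Separately,** bring the Table 1 crestal entry into line with the pre-extraction film.

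The cost is mainly wording. Each model uses one residual degree of freedom (31 instead of 32). The average SE penalty is at most 1.7%, and about 6% for a two-SE imbalance when k·rho = 1. If a baseline crestal reading is chosen, it means up to 34 readings of films already taken.
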